## **8.7.2 Appropriateness of Measurements**

The efficacy and safety assessments are widely used and generally recognized as reliable, accurate, and relevant to the disease condition.

## **8.8 Statistical Methods**

### **8.8.1 Statistical and Analytical Plans**

A detailed statistical analysis plan will be created and finalized prior to the interim database lock and the final database lock.

#### **8.8.1.1 Datasets or Populations Analyzed**

All randomized subjects who received at least one dose of study medication and have at least one post-Baseline efficacy assessment will be included in the efficacy analysis (intent-to-treat [ITT]).

A secondary per-protocol analysis will be performed to confirm the ITT analysis, excluding subjects with major protocol deviations (such as Baseline CRP within normal range, Baseline TJC68 <8, Baseline SJC66 <6, <80% study medication compliance, or use of forbidden concomitant medications). Full details of the major protocol deviations will be described in the statistical analysis plan, with adherence to analysis sets agreed upon prior to database lock and unblinding.

All randomized subjects who received at least one dose of study medication will be included in the safety analysis.

All randomized subjects who received at least one dose of GLPG0634 and who have at least one PK measurement will be included in the PK analysis.

Reasons for study termination will be tabulated.

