#### **8.3.2 Inclusion Criteria**

To be eligible for study entry subjects must fulfil all of the following criteria:

1. Male or female subjects who are  $\geq 18$  years of age on the day of signing informed consent.
2. Diagnosis of RA since at least 6 months prior to Screening and meeting the 2010 ACR/EULAR criteria of RA and ACR functional class I-III.
3. Have  $\geq 6$  swollen joints (from a 66-joint count) and  $\geq 8$  tender joints (from a 68-joint count) at Screening and Baseline.
4. Screening serum CRP  $\geq 0.7$  x upper limit of the normal (reference) laboratory range (ULN).
5. Have shown an inadequate response in terms of either lack of efficacy or toxicity to MTX.
6. Have agreed to be washed out from MTX for a period of at least 4 weeks before or during the Screening period.
7. If taking oral steroids, these should be at a dose  $\leq 10$  mg/day of prednisone or prednisone equivalent and stable for at least 4 weeks prior to Baseline.
8. If taking non-steroidal anti-inflammatory drugs (NSAIDs), these must be at a stable dose for at least 2 weeks prior to Baseline.
9. The results of the following laboratory tests performed at the central laboratory at Screening must be within the limits specified below:
  - a) Hemoglobin  $\geq 10$  g/dL (International System of Units [SI]:  $\geq 100$  g/L);
  - b) WBCs  $\geq 3.0 \times 10^3$  cells/mm^3 (SI:  $\geq 3.0 \times 10^9$  cells/L);
  - c) Neutrophils  $\geq 2.0 \times 10^3$  cells/mm^3 (SI:  $\geq 2.0 \times 10^9$  cells/L);
  - d) Lymphocytes  $\geq 1.0 \times 10^3$  cells/mm^3 (SI:  $\geq 1.0 \times 10^9$  cells/L);
  - e) Platelets  $\geq 100 \times 10^3$  cells/mm^3 (SI:  $\geq 100 \times 10^9$  cells/L);
  - f) Serum ALT and aspartate aminotransferase (AST)  $\leq 1.5$  x ULN;
  - g) Total bilirubin level  $\leq 1.25$  x ULN;
  - h) Alkaline phosphatase  $\leq 1.5$ ULN;
  - i) Lipase  $\leq 1.5$  x ULN and amylase  $\leq 1.5$  x ULN;
  - j) Creatinine clearance  $>60$  mL/min. Creatinine clearance will be calculated using the Cockcroft-Gault formula.
10. Female subjects must have a negative pregnancy test unless they are surgically sterile or have been post-menopausal for at least one year (12 consecutive months without menses); in case of doubt a determination of serum FSH can be done with FSH levels above 35 mIU/mL being confirmative for menopause.

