**8.7.1.5 Flow Chart**

Event	Screening	Baseline 	Treatment period 									FU visit 
			D8/ W1	D15/ W2	D29/ W4	D57/ W8	D85/ W12	D113/ W16	D141/ W20	D169/ W24	EDV 	
Informed consent	Written informed consent will be obtained before any study-related procedures and/or assessments are performed.											
Inclusion/ exclusion criteria	X	X 										
Demographic data and baseline disease characteristics	X											
Medical history/ concomitant illnesses	X											
Physical examination	X 	X					X			X	X	X
Serology 	X											
TB test and chest X-ray 	X											
Pregnancy test 	X	X	X	X	X	X	X	X	X	X	X	X
12-Lead ECG	X						X			X	X	X
Vital signs 	X	X	X	X	X	X	X	X	X	X	X	X
Clinical laboratory tests 	X	X	X	X	X	X	X	X	X	X	X	X
PK samples  blood					X		X			X	X	
PD samples  blood		X	X		X		X			X	X	

 Subjects will begin to take their treatment on the next morning (Day 1) following randomization.

 During the treatment period, a visit time window of  $\pm 2$  calendar days is allowed.

 Follow-up visit will be performed only for subjects discontinuing prematurely from the study and for subjects not entering the Long Term Follow-up study GLPG0634-CL-205.

 Early discontinuation visit.

 Eligibility criteria check based on the laboratory results from the Screening visit.

 At Screening, includes height and weight.

 Includes Hepatitis B and C, HIV 1 and 2, RF, and anti-CCP.

 X-ray should be performed if results from an X-ray performed in the previous 3 months are not available at the site.

 For female subjects only. To be performed on serum at Screening and Week 24/EDV and on urine for other visits.

 Vital signs are defined as blood pressure (systolic and diastolic), HR, and oral temperature.

 Refer to Section 8.7.1.4.2.

 PK samples: 1 blood sample (2 mL) for analysis of GLPG0634 and its main metabolite (G254445) in plasma.

 PD samples: 4 blood samples (2x4 mL for serum preparation and 2x2.5 mL in PAXgene tubes) will be collected for analysis of serum (analytes and miRNA profiling) and whole blood (gene expression in circulating leukocytes, mRNA and miRNA profiling).

CONFIDENTIAL

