2.1.1. Efficacy data

Study period	Treatment groups	Analysis populations	Imputation method
“Chapter 2”: Periods 1+2 together (full 24 weeks period)	
The 4 original groups:
 
 – Placebo¹ – GLPG0634 50 mg q.d. – GLPG0634 100 mg q.d. – GLPG0634 200 mg q.d. 
For the subjects in the placebo and low dose groups who switched to 100 mg/day during the second study period: they will be handled as if they discontinued at Week 12, and will be imputed from Week 12 onwards in the second study period. (Details: see further in the SAP)
	
ITT: all subjects randomized, exposed at least once, and with post-baseline data for at least one efficacy parameter.
 
Per-protocol: subpopulation of ITT, excluding all critical (=major) protocol deviations. This is decided during the blind review meeting before final database lock.
	
Observed case, non-responder imputation (NRI), last observation carried forward (LOCF): depending on the parameter; is specified later when all parameters are discussed.

¹ Note that all placebo subjects switch to 100 mg q.d. after Week 12. As a result, no “placebo” group will be presented after Week 12 in the tables and figures.

Study period	Treatment groups	Analysis populations	Imputation method

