6.3. CHANGES TO THE PLANNED ANALYSES, NOT COVERED BY PROTOCOL AMENDMENTS

6.3.1. Changes before Interim Database Lock

No changes to the protocol-specified analyses were made. The SAP provides further elaborations, clarifications and specifications on the protocol-specified analyses.

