7.2. PROTOCOL DEVIATIONS AND ELIGIBILITY

Protocol deviations are determined and recorded whilst the study is ongoing, and the list is finalized prior to database lock (and unblinding). All deviations are classified as either “critical” or “non-critical”. Only the critical (=major) protocol deviations will be presented in the tables. For more details, please refer to the Protocol Deviation Plan.

Table 14.1.2.1: Major protocol deviations

Tabulation per treatment group (and overall) of the number (and percentage) of subjects having a major/minor protocol deviation, together with the detailed protocol deviation categories of the major deviations only.

Population: safety.

Listing 16.2.2.1: Protocol deviations

Listing per treatment group and per subject of all protocol deviations, with indication critical/non-critical.

Population: safety.

Listing 16.2.2.2: Eligibility criteria: Violations

Only violated in- and exclusion criteria will be listed per treatment group and per subject. These are criteria as ticked by the investigator in the eCRF.

Population: safety.

Listing 16.2.2.3: Final eligibility statements

Listing per treatment group and per subject of the final eligibility statements in the eCRF at screening and at baseline.

Population: safety.

7.3. SUBJECTS EXCLUDED FROM ANALYSIS**Listing 16.2.3.1: Subjects excluded from the safety analysis**

Listing of all subjects that were randomized and/or not treated: the trial termination reason and/or the reason for being a no-treatment subject will be listed, whichever is available.

Population: all screened population, minus the Safety population.

Listing 16.2.3.2: Subjects excluded from the efficacy ITT analysis

Listing of all subjects that were exposed but who were not included in the ITT population: the trial termination reason and the reason for being excluded will be listed.

Population: Safety, minus the ITT population.

Listing 16.2.3.3: Subjects excluded from the efficacy per-protocol analysis

Listing of all subjects that were in the ITT population but not in the per-protocol population: the trial termination reason and the reason for being excluded will be listed.

Population: ITT population, minus the Per-protocol population.

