8.8. ACR COMPONENT: SERUM CRP

8.8.1. Parameters

Serum CRP (mg/L) will be analyzed as raw values, change from baseline and percent change from baseline.

Note that if for a specific visit both the regular CRP as well as the high-sensitive CRP are available, the high-sensitive CRP will be used in the analysis tables and figures. The regular CRP will then only be listed.

CRP and hsCRP values will also be categorized according to the lab's normal ranges: normal (value \leq ULN) or high (value $>$ ULN), where ULN = upper limit of the normal range as provided by the central lab. Note that the same ULN (8.999) will be applied to both CRP and hsCRP.

Note that CRP and hsCRP will be excluded from the lab safety analysis.

Note that the percentage change from baseline remains missing if the baseline value itself equals zero.

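### The protocol's per-protocol exclusion for a normal Baseline CRP contradicts its own entry criterion, and the SAP does not settle which applies

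*Protocol*

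**What the plan says.** Protocol 8.8.1.1 plans a secondary per-protocol analysis to confirm the ITT result, "excluding subjects with major protocol deviations (such as Baseline CRP within normal range, Baseline TJC68 <8, Baseline SJC66 <6", followed by poor compliance and forbidden medication. It then says: "Full details of the major protocol deviations will be described in the statistical analysis plan".

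The only CRP entry rule is inclusion criterion 4 in Protocol 8.3.2: "Screening serum CRP $\geq 0.7$ x upper limit of the normal (reference) laboratory range (ULN"). The synopsis gives the same threshold. For laboratory criteria, the re-check at the Baseline visit looks back to Screening; Flow Chart footnote 5 (Protocol 8.7.1.5) reads: "Eligibility criteria check based on the laboratory results from the Screening visit".

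SAP 2.1.1 defines per-protocol as ITT minus critical (major) deviations and says of membership: "This is decided during the blind review meeting before final database lock". SAP 7.2 sends the reader elsewhere: "For more details, please refer to the Protocol Deviation Plan". SAP 6.3.1 states: "No changes to the protocol-specified analyses were made". The later changes listed in SAP 6.3.2 do not touch the per-protocol set.

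**The concern.** A protocol deviation should be a departure from something the protocol requires. The two joint-count examples in 8.8.1.1 meet that test, because criterion 3 requires at least 8 tender and 6 swollen joints at both Screening and Baseline. The CRP example does not, because nothing requires a raised CRP at Baseline. Amendment 5 revised criterion 4 and left 8.8.1.1 unreconciled with it.

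If the example is applied, subjects who complied with the protocol leave the set that is meant to represent compliance. The per-protocol set then carries two restrictions at once, adherence and inflammatory activity at Baseline. A difference between the per-protocol and ITT results could come from either, so the analysis loses its value as confirmation. The results exposed are per-protocol ACR20 (Tables 14.2.1.1.1 and 14.2.1.1.2), DAS28(CRP) (Tables 14.2.1.4.1 to 14.2.1.4.5) and EULAR response (Tables 14.2.1.4.12 and 14.2.1.4.13).

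Timing is a further reason to write the rule down. ACR20 by arm and Baseline CRP category (Table 14.2.1.1.7) is also produced for the unblinded Week 12 interim. The sponsor sees those summaries, although the study team stays blinded. Per-protocol membership is decided later, before final lock.

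**Working it through.** **1. Do the rules conflict?**

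| | Entry rule | Deviation example in 8.8.1.1 | Match |
|---|---|---|---|
| Tender joints (68) | at least 8 at Screening and Baseline | Baseline below 8 | yes |
| Swollen joints (66) | at least 6 at Screening and Baseline | Baseline below 6 | yes |
| CRP | Screening at least 0.7 x ULN; no Baseline level | Baseline within normal range | no |

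On the ULN, SAP 8.8.1 says: "Note that the same ULN (8.999) will be applied to both CRP and hsCRP". The same section classes a value at or below ULN as normal. The entry threshold is 0.7 x 8.999 = 6.30 mg/L. Two kinds of eligible subject would be classed as major deviators:

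- CRP stable between 6.30 and 8.999 mg/L at both visits;
- CRP raised at Screening but at or below 8.999 mg/L at Baseline.

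The SAP provides for such subjects. Its Baseline CRP categories include below 0.7 x ULN and 0.7 to 1.0 x ULN (SAP 7.5.1 and Table 14.2.1.1.7), and Table 14.2.1.8.3 splits results at the ULN.

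**2. Reproducing the plan's power**

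Protocol 8.8.2 gives n = 70 per arm, alpha = 5%/3 per comparison, a chi-square approach, and 90% power for 43% versus 15% and for 70% versus 40%. Sidedness is not stated; two-sided is assumed, so z = 2.394.

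Power = Φ{[d√n − z√(2p̄(1−p̄))] / √[p₀(1−p₀) + p₁(1−p₁)]}, where d = p₁ − p₀ and p̄ is the mean of the two rates.

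For 43% versus 15%: d√n = 0.28 x 8.367 = 2.343; z√(2 x 0.29 x 0.71) = 2.394 x 0.6417 = 1.536; denominator √(0.1275 + 0.2451) = 0.6104. Power = Φ(0.806/0.6104) = Φ(1.321) = 90.7%. For 70% versus 40% the result is 89.1%. Both agree with the stated 90%. A one-sided test would give 94.5% and 93.4%, which does not fit.

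**3. Size if the example is applied**

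The documents do not give the share f of subjects with Baseline CRP at or below ULN. The values below are assumptions, with equal loss in every arm, unchanged response rates and no other exclusions. n = 70(1−f); the SE of a difference grows by 1/√(1−f).

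| f (assumed) | n per arm | SE factor | Power, 43% vs 15% | Power, 70% vs 40% |
|---|---|---|---|---|
| 0 | 70 | 1.000 | 90.7% | 89.1% |
| 10% | 63 | 1.054 | 87.0% | 85.1% |
| 20% | 56 | 1.118 | 82.0% | 79.8% |
| 30% | 49 | 1.195 | 75.6% | 73.2% |

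**The case against.** The strongest case is about reach and about what cannot be seen.

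- **Reach.** Per-protocol is a supportive set. ACR50, ACR70, SDAI/CDAI and the observed-case analyses are ITT only, and so are the interim ACR20 and DAS28(CRP) tables. No power target is set for the per-protocol set, so the fall in power misses no stated requirement. This stands, and it keeps the point well below a threat to the trial's main conclusion.
- **Application is uncertain.** The list in 8.8.1.1 is illustrative, and the Protocol Deviation Plan, which is not among the documents, may already settle the matter before lock. SAP 6.3.1 shows neither that the example is kept nor that it is dropped, since it goes on to say that the SAP adds clarifications. This also stands: the mismatch is certain, its application is open. But the item is named explicitly and never withdrawn, and the protocol gave the task of defining deviations to the SAP.
- **The source would be visible.** Listing 16.2.3.3 gives the reason for each exclusion, Table 14.1.2.1 tabulates major-deviation categories by arm, Table 14.1.3.7 shows Baseline CRP categories in each population, and Table 14.2.1.4.6 breaks DAS28(CRP) change down by Baseline CRP. A reader could count the CRP exclusions. None of these outputs gives a per-protocol estimate without them.
- **Another resolution exists.** The sponsor could keep the exclusion as a deliberate restriction. That is possible, but it would then be a restricted-activity set and should carry that label, not the label of protocol deviation.

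**Conclusion.** The concern holds. As written, the protocol classes subjects who satisfied every entry rule as major deviators, and the SAP leaves open whether that will be done. This is a conflict between two stated rules, not just a missing detail.

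The consequence is limited to interpretation and precision of the per-protocol ACR20, DAS28(CRP) and EULAR response results. The exclusion rests on a pre-treatment value, so it does not by itself bias the randomized comparison. The primary analysis (ACR20 at Week 12, ITT, non-responder imputation) and the power in Protocol 8.8.2 are unchanged. The size depends entirely on the share of subjects with normal Baseline CRP. Over an assumed 10% to 30%, the standard error of a difference rises by 5% to 20%. It should be settled before blind review.

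**What to change.** Before the blind review meeting, add one statement to the SAP (2.1.1 or 7.2) and to the Protocol Deviation Plan: the CRP-related major deviation is a Screening CRP below the criterion 4 threshold of the protocol version in force when the subject enrolled (0.7 x ULN under Amendment 5), and a Baseline CRP within the normal range is not a deviation. Tying the rule to the version in force avoids judging earlier or later entrants against a criterion that did not apply to them.

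Delete the Baseline CRP example from Protocol 8.8.1.1 at the next amendment. That can wait, because 8.8.1.1 already delegates the details to the SAP.

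The cost is a short clarification in two documents. No new data or analysis is needed: Table 14.2.1.1.7 already shows ACR20 by Baseline CRP category in ITT, which answers the question of response in subjects with normal CRP.

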#### **8.8.1.2 Demographic and Other Baseline Characteristics**

Demographic characteristics will be listed. Demographic characteristics will be summarized using appropriate descriptive statistics, as applicable. Details of the summaries to be produced will be included in the statistical analysis plan.

#### **8.8.1.3 Efficacy Variables**

##### **Definition of Primary Efficacy Endpoint – ACR20 at Week 12**

The primary endpoint is the percentage of subjects achieving an ACR20 response at Week 12. Other time points will be regarded as secondary endpoints.

The ACR response is a measurement of improvement in multiple disease assessment criteria. The ACR20 response is defined as:

≥20% improvement from Baseline in SJC66 (66 joints) and TJC68 (68 joints)

AND

≥20% improvement from Baseline in at least 3 of the following 5 assessments

CONFIDENTIAL

- Pain (VAS) in cm (from HAQ-DI).
- Patient's Global Assessment of Disease Activity (VAS) in cm.
- Physician's Global Assessment of Disease Activity (VAS) in cm.
- Patient's Assessment of Physical Function as measured by HAQ-DI.
- CRP in mg/dL or mg/L.

### **Definition of Secondary Efficacy Endpoints**

#### **ACR50 and ACR70**

ACR50 and ACR70 are defined similarly to ACR20, except the improvement threshold from Baseline is 50% and 70%, respectively.

#### **ACR-N**

The ACR-N is the smallest percentage improvement in swollen and tender joints and the median of the remaining 5 core parameters, and is expected to be more sensitive to change than the ACR20, ACR50 or ACR70.

ACR-N = MIN [%improvement in TJC68,  
                  %improvement in SJC66,  
                  MED %improvement in (Patient's Global Assessment, Physician's  
                  Global Assessment, HAQ-DI, CRP)]

#### **ACR/EULAR Remission**

A subject's disease activity status can be defined as being in remission:

when scores on the TJC28, SJC28, CRP (actual value in mg/dL) and Patient Global Assessment of Disease Activity (cm) are all ≤1.

#### **Simplified Disease Activity Index (SDAI)**

The SDAI is the numerical sum of 5 outcome parameters: TJC28, SJC28, Patient Global Assessment of Disease Activity (in cm), Physician's Global Assessment of Disease Activity (in cm) and CRP (mg/dL).

SDAI = TJC28 + SJC28 + Patient's Global Assessment of Disease Activity (VAS in cm) + Physician's Global Assessment of Disease Activity (VAS in cm) + CRP (mg/dL)

The SDAI can be categorized:

- High disease activity: SDAI >26
- Moderate disease activity: [11,26]
- Low disease activity: [3.3,11]
- Remission: ≤3.3

#### **Clinical Disease Activity Index (CDAI)**

The CDAI is the SDAI modified to exclude CRP.

CDAI = TJC28 + SJC28 + Patient's Global Assessment of Disease Activity (VAS in cm) + Physician's Global Assessment of Disease Activity (VAS in cm)

The CDAI can also be categorized:

- High disease activity: >22
- Moderate disease activity: [10,22]
- Mild disease activity: [2.8,10]
- Remission: ≤2.8

### **Disease Activity Score Based on 28 Joints Corrected for C-reactive Protein (DAS28[CRP])**

The DAS28(CRP) is a statistically derived index combining tender joints (28 joints), swollen joints (28 joints), CRP, and Patient's Global Assessment of Disease Activity (general health, GH). DAS28(CRP) is defined as follows:

$$\text{DAS28(CRP)} = 0.56 \times \text{SQRT(TJC28)} + 0.28 \times \text{SQRT(SJC28)} + 0.36 \times \text{Ln(CRP+1)} + 0.014 \times \text{GH} + 0.96,$$

Where:

TJC28 is 28-joint count for tenderness

SJC28 is 28-joint count for swelling.

Ln(CRP+1) is the natural logarithm of (CRP value [mg/L] + 1)

SQRT is square root

GH is the Patient's Global Assessment of Disease Activity on a 100 mm VAS

Categorization of the DAS28(CRP) scores:

High disease activity: >5.1

Moderate disease activity: [3.2,5.1]

Low disease activity: [2.6,3.2]

Remission: <2.6

### **EULAR Response**

A second categorization of the DAS28(CRP) will be done according to the following table:

Actual DAS28(CRP)	Improvement in DAS28(CRP) from Baseline:		
	> 1.2	> 0.6, ≤ 1.2	≤ 0.6
≤ 3.2	Good	Moderate	None
> 3.2, ≤ 5.1	Moderate	Moderate	None
> 5.1	Moderate	None	None

### **Quality of Life - FACIT Fatigue Scale and SF-36**

Quality of life will be assessed using the FACIT fatigue scale and the SF-36 questionnaire. The appropriate (sub)totals will be derived according to the scale's scoring algorithm.

---

## **Methods of Analysis**

Efficacy data (ACR20, ACR50, ACR70, ACR-N, DAS28[CRP]), EULAR response, and ACR/EULAR remission, and components of the ACR, CDAI and SDAI at each post-dosing visit) will be analyzed descriptively.

Between-group comparisons will be done for each dose group versus the placebo group. Hommel's closed-testing correction procedure (as implemented in SAS PROC MULTTEST) will be applied to adjust for multiplicity.

This study is not powered for any formal comparison among the GLPG0634 dose groups. However, differences between the dose groups will be calculated and presented with a 95% confidence interval. No adjustment for multiplicity will be done for these exploratory differences.

All subjects from the placebo group and nonresponding subjects from the 50 mg group who are reassigned to 100 mg at Week 12 will be handled as follows:

- Their Week 12 value will be carried forward in the original treatment group to all further time points (and between-group comparisons) after Week 12.
- Their actual assessments on Weeks 16, 20, and 24 will be analyzed descriptively as these represent their response after 12 weeks of GLPG0634 exposure after first having received placebo or failed on a low dose.

Analysis methods per post-Baseline time point:

- Binary parameters: logistic regression model with factors treatment, region and previous use of biologics.
- Continuous parameters: changes from Baseline and percent changes from Baseline: using an analysis of (co)variance model with factors treatment, baseline value, region and previous use of biologics.
- Time to response (ACR20/50/70) will be analyzed using Kaplan-Meier survival techniques, and groups will be compared against placebo using a Cox proportional hazards regression model with factors treatment, region and previous use of biologics.

Other applicable factors, if any, will also be included in the models. Quality of life data (FACIT fatigue scale and SF-36 questionnaire) will be analyzed descriptively. Exploratory between-group comparisons will also be done at each post-Baseline time point using analysis of (co)variance models on the changes from Baseline with factors treatment, Baseline value, region and previous use of biologics.

Handling of discontinued subjects during the 24-week treatment period:

- Subjects who discontinue within the first week so that ACR20/50/70 responses cannot be determined will be classified as nonresponders.
- For all discontinued subjects, their last observed non-missing result will be used in the subsequent visits (last observation carried forward algorithm) and for the ACR20/50/70 responses as part of the secondary/supportive analyses.

A descriptive sensitivity analysis by country, geographic region and previous use of biologics will be performed for the ACR criteria response rates.

CONFIDENTIAL

Further exploratory analyses may be added when deemed useful to understand the data.

Graphical presentations may be added to facilitate the overall interpretation of the study results.

